**Testing a Training Program That uses Virtual Reality Technology to Improve Children's
Pedestrian Behaviors: A Randomized Controlled Trial**

#NCT-03960047

Sept 1 2019

TITLE

Testing a Training Program That uses Virtual Reality Technology to Improve Children's Pedestrian Behaviors: A Randomized Controlled Trial

NCT-03960047

SETTING

We focus on midblock crossing on two-lane bidirectional roads, without nearby traffic signals or crosswalks.

For SS-T sessions, a road has been identified (50 km limit) that provides opportunity for training in *where* and *how* to cross in the same types of road situations to be presented in VR-T. Traffic volume was recently measured for 7 days and varied from light (8 cars/min) to heavy (16 cars/min).^{13,30} This range for traffic volume will occur in VR-T.

For VR-T sessions, these occur in the VR lab at UG campus.

For pre and post measures, for all groups these occur in two settings: **(a)** street side (designated as "Field" below) with naturally varying traffic (children indicate where and how they will cross but do not do so), **(b)** in the VR lab in which children cross the virtual street in traffic using a gaming controller.

Note that the pre/post Field measures will be taken at two locations along the *same* road (randomized order, with one used for pre and the other for post), which controls for familiarity and minimizes risk of large variation in traffic volume between pre/post measures. The road is nearby the VR lab, which allows children to complete pre-test VR *and* Field measures during the *same* visit to UG; the same will occur for post-test measures. Posted speed is 50 km, which means traffic conditions to be tested on are ones that pose risk of severe injury at these ages.^{13,57}

TESTING PROTOCOL

Pre/Post measures for Where and How to Cross

[Note that pre- and post- measures are the same, and all children, regardless of group, complete all measures.]

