Behaviors. We will document the baseline characteristics of each of the 3 groups (age, sex, walking experience, days between pre- and post- tests, family income, and traffic volume for field measures). We will produce point estimates and confidence intervals for the mean difference between pre- and post-immediate scores (i.e., change scores) for each group and each *where* (1 score), *how* (3 scores), and *consequence* (2 scores) outcome. We will then use linear regression of change score on group adjusting for covariates. We will extend this approach to multivariate (modeling multiple outcomes) linear regression incorporating all of the outcomes into one model and employing an adjustment for multiple comparisons. We will include interaction terms between group and sex to determine if child sex modifies program effects. An intention-to-treat approach will be followed. The goal is to assess for immediate gains following program completion in our outcomes (for Sustainability see Secondary Analyses).

Secondary Analyses

Behaviors. These will examine pre- to post-immediate changes in *Component Skills* performance (e.g., *where*: selecting safe location with parked cars) and examine from post-immediate to post-2 months later (to assess for sustainability of effects), comparing pre to post scores using the same approach as above.

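### Sustainability is tied to change from post-immediate to 2 months, which measures decay; the reference visit is ambiguous, and the between-group benefit remaining at 2 months should be named as the estimate

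*Combined protocol and SAP*

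**What the plan says.** The Primary Analyses section of the SAP plans, for three groups, "point estimates and confidence intervals for the mean difference between pre- and post-immediate scores (i.e., change scores) for each group" on one where, three how and two consequence scores. The between-group step follows: "We will then use linear regression of change score on group adjusting for covariates". The section then limits its own scope: "The goal is to assess for immediate gains following program completion in our outcomes (for Sustainability see Secondary Analyses").

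The Secondary Analyses section opens with component skills ("These will examine pre- to post-immediate changes in" those skills). The same sentence then turns to sustainability: "from post-immediate to post-2 months later (to assess for sustainability of effects), comparing pre to post scores using the same approach as above". This is the only mention of a 2-month assessment in the document.

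The Testing Protocol says that "all children, regardless of group, complete all measures", but speaks only of pre and post measures. The Setting section describes two Field locations, "with one used for pre and the other for post", and none for a later visit.

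**The concern.** A sustainability analysis should tell a reader whether trained children still do better than their comparators 2 months after training. The interval that the SAP names answers a neighbouring question: whether the groups change differently after training ends. Decay is worth estimating, but a flat post-training course fits a lasting benefit and a program with no effect equally well.

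The final words of the sentence add a second difficulty. Comparing pre with post may mean the visit before training against the 2-month visit, or the earlier against the later of the two visits just named. These are different estimands. If the choice is left open, it can be made after results are seen.

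The conclusion about lasting benefit is what is at stake. On the decay reading, the report would show a gain and a loss without a direct interval for what is left, and a non-significant loss could be taken for a sustained benefit.

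**Working it through.** The documents give no sample size, SD, effect or retention figure, so there is no stated figure to reproduce. The check is algebra, followed by an illustration on assumed inputs.

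**1. The three contrasts.** Let P, I and M be the difference in mean score, trained minus comparator, at pre-test, post-immediate and 2 months.

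- Immediate effect (primary analysis): I − P
- Post-immediate to 2 months (the interval named): M − I
- Pre to 2 months (the other reading): M − P = (I − P) + (M − I)

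The two readings of the sustainability clause differ by I − P, the whole immediate effect.

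**2. What each reading returns.** Assume an immediate gain of 0.5 SD, an unchanged comparator and a share k of the gain kept. Then M − I = −(1 − k) × 0.5 and M − P = k × 0.5.

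| Case | Immediate | Post-immediate to 2 months | Pre to 2 months |
|---|---|---|---|
| All kept (k = 1) | 0.50 | 0.00 | 0.50 |
| Half kept (k = 0.5) | 0.50 | −0.25 | 0.25 |
| None kept (k = 0) | 0.50 | −0.50 | 0.00 |
| Never worked | 0.00 | 0.00 | 0.00 |

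The first and last rows cannot be told apart by the decay contrast. This result does not depend on the 0.5 SD.

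**3. How the decay contrast behaves as a significance test (all inputs assumed).** Take one pair of groups, unit SD, n = 50 per group, correlation r = 0.5 between adjacent visits, a two-sided 5% t-test and no multiplicity adjustment. The variance of one child's change is 2(1 − r), so the SE of the contrast is √(4(1 − r)/n) = √(4 × 0.5/50) = 0.200. Ranges in brackets cover n = 30 to 80 and r = 0.3 to 0.7.

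- Gain 0.8 SD, half lost: contrast −0.40, or 2.00 SE. Decay is non-significant in 49% of trials (10 to 75%).
- Gain 0.5 SD, half lost: contrast −0.25, or 1.25 SE. Non-significant in 76% (47 to 87%).
- Gain 0.8 SD, 70% kept: contrast −0.24, or 1.20 SE. Decay is significant in 22% (12 to 50%), although 0.7 × 0.8 = 0.56 SD of benefit remains.

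**4. The pre to 2-month contrast on the same inputs.** Its SE is 0.200 if correlation is equal across visits, and √(4(1 − r²)/n) = √(4 × 0.75/50) = 0.245 if correlation decays with time. It detects a remaining 0.56 SD in 79% or 62% of trials, and a remaining 0.40 SD in 51% or 37%. It is no sharper in general; it answers a different question.

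**5. Could a reader add the two planned estimates?** The sum gives the right point estimate. Treating the two as independent gives SE √(0.200² + 0.200²) = 0.283, which is 0.283/0.200 = 1.41 or 0.283/0.245 = 1.15 times too large, because both use the post-immediate score. Detection of the remaining 0.56 SD falls to 50%.

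**The case against.** The strongest reply is that the pre to 2-month comparison may already be planned. Elsewhere the document uses pre for the visit before training, and on that usage the end of the sentence supplies most of the fix. This stands as a reading. It does not settle the matter, because the interval named in the same sentence begins at post-immediate.

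A reader might go further and infer that no between-group analysis at 2 months is planned. The documents do not support that: the approach carried over includes "linear regression of change score on group adjusting for covariates". Nor is the lack of an express between-group interval peculiar to 2 months. Even in the primary analysis, intervals are promised in words only for change within each group, and a regression coefficient normally comes with one.

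A reader might also infer that the investigators will declare benefit sustained whenever the decay test is non-significant. The SAP states no such rule, nor any plan to add the two estimates as independent. Steps 3 and 5 of the working therefore show what could go wrong in interpretation, not what the plan prescribes. Their inputs are all assumed and the ranges are wide. Much of the uncertainty comes from the assumed sample size rather than the choice of contrast: with a 0.8 SD gain half lost, the decay contrast detects the loss in 51% of trials, and the pre to 2-month contrast detects the remainder in 51% or 37%.

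Finally, the outcomes covered are less obscure than they first appear. The pointer from the Primary Analyses suggests that the where, how and consequence scores are meant.

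**Conclusion.** The point holds in a limited form. The one interval named for sustainability yields differential decay, which does not by itself show whether a trained group is still better at 2 months, and the wording leaves the reference visit open. That conclusion rests on the text and the identity in step 1, not on assumed numbers. The gap between the readings equals the immediate effect, whatever its size; the percentages rest on assumed sample size, SD, correlation, effect and retention.

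The documents do not support calling the decay analysis invalid. It is a legitimate secondary question, and a significant result would be a correct finding of loss, though not evidence that all benefit has gone. The primary result is untouched. Severity is minor to moderate: a secondary analysis, but the only one that addresses sustainability.

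**What to change.** In the Secondary Analyses, state the reference visit and name the sustainability estimate. For each group assessed at 2 months, this is the between-group difference in pre to 2-month change, with a confidence interval, for the where, how and consequence scores. That keeps the SAP's change-score method; the 2-month score adjusted for pre-test is an alternative. Retain the post-immediate to 2-month change, within and between groups, as the measure of decay, and state that a non-significant decay contrast will not be read as sustained benefit.

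The cost is extra secondary analysis. Three groups give up to 3 pairwise contrasts on each of 6 scores, so 3 × 6 = 18 in one setting and 18 × 2 = 36 if Field and VR are analysed separately. Place these under the multiple-comparison adjustment already planned, or label them exploratory.

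No new data are needed for groups already assessed at 2 months. The documents do not describe that visit, so the SAP should say which groups attend it; for any group that does not, the contrast is unavailable.
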